## LIST OF ABBREVIATIONS

Abbreviation	Definition
AE	Adverse event
AML	Acute myeloid leukemia
ALT	Alanine aminotransferase
AST	Aspartate aminotransferase
AUC	Area under the curve
BMMC	Bone marrow mononuclear cell
BUN	Blood urea nitrogen
CFR	Code of Federal Regulations
CHF	Congestive heart failure
CI	Confidence interval
CL	Oral clearance
C max	Maximum concentration
CMML	Chronic myelomonocytic leukemia
CNS	Central nervous system
CR	Complete remission
CRO	Contract Research Organization
Cys	Cysteine
DLT	Dose-limiting toxicity
DOCR	Duration of complete remission
DOR	Duration of response
DRM	Data review meeting
DRT	Data Review Team
EC	European Commission
ECG	Electrocardiogram
ECOG	Eastern Cooperative Oncology Group
eCRF	Electronic Case Report Form
EDC	Electronic data capture
EE	Efficacy-evaluable
FDA	Food and Drug Administration
FIH	First-in-human
GCP	Good Clinical Practice
GSH	Glutathione
HI	Hematological improvement
HMA	Hypomethylating agent
HSCT	Hematopoietic stem cell transplantation
IB	Investigator's Brochure
ICH	International Council for Harmonization
IEC	Independent Ethics Committee
IPSS	International Prognostic Scoring System
IPSS-R	Revised International Prognostic Scoring System

IRB	Institutional Review Board
i.v.	Intravenous
IWG	International Working Group
LFT	Liver function test
mBED	Minimum biologically effective dose
mCR	Marrow complete response
MDS	Myelodysplastic syndrome
MQ	2-methylene-quinuclidin-3-one
NCI-CTCAE	National Cancer Institute Common Terminology Criteria for Adverse Events
NGS	Next-generation sequencing
NOAEL	No-observed-adverse-effect level
OS	Overall survival
ORR	Overall response rate
PBMC	Peripheral blood mononuclear cell
PD	Pharmacodynamic(s)
PK	Pharmacokinetic(s)
p.o.	Orally ( per os )
popPK	Population pharmacokinetics
PR	Partial remission
PRBC	Packed red blood cells
QD	Once daily ( quaque die )
QTcF	Corrected QT interval by Fridericia formula
RBC	Red blood cell
RFS	Relapse-free survival
RP2D	Recommended phase 2 dose
SAE	Serious adverse event
s.c.	Subcutaneous
SCT	stem cell transplantation
SD-OCT	Spectral domain optical coherence tomography
SOC	System Organ Class
TEAE	Treatment-emergent adverse event
T max	Time to maximum concentration
TrxR1	Thioredoxin reductase 1
T 1/2	Half-life
TI	Transfusion independence
ULN	Upper limit of normal
US	United States
USPI	United States Prescribing Information
VAF	Variant allele frequency
V d /F	Volume of distribution
WHO	World Health Organization

## 1.0 GENERAL INFORMATION

### 1.1 Protocol Number and Title of the Study

Protocol No. A20-11202

Protocol Title: Phase 1 Study to Evaluate the Safety and Efficacy of APR-548 in Combination with Azacitidine for the Treatment of *TP53*-Mutant Myelodysplastic Syndromes

## 2.0 BACKGROUND INFORMATION

### 2.1 Disease Background

Myelodysplastic syndromes (MDS) are a heterogeneous group of neoplasms arising from a clonal hematopoietic precursor. MDS is characterized clinically by cytopenia and a tendency to transform to acute myeloid leukemia (AML). Prognostic scoring systems have been developed to help stratify patients based on predicted survival and progression to AML. In practice, treatment decisions are made by grouping patients with MDS into lower and higher risk subgroups as defined by clinical prognostic scoring systems. Specifically, the International Prognostic Scoring System (IPSS) and its more modern version, the revised-IPSS (IPSS-R), represent the most widely used clinical prognostic tools. Those patients that fall in the higher risk group have an expected survival of less than 12 months if left untreated and progress to AML greater than 30% of the time.

## 2.2 *TP53* Mutations in MDS

Patients with higher risk MDS fall into IPSS categories of intermediate-2-risk and high-risk groups, corresponding largely to IPSS-R groups very high, high, and, sometimes, intermediate.

To date, the only disease modifying agents in MDS include lenalidomide in patients with isolated deletion of 5q (del(5q)) and the hypomethylating agents (HMA) azacitidine and decitabine.

For higher risk MDS patients, azacitidine represents the standard of care based on the AZA-001 trial that demonstrated a survival advantage for azacitidine when compared with induction chemotherapy, low dose cytarabine, or best supportive care (24.5 months versus 15 months,  $p<0.0001$ ).

The advent of next-generation sequencing (NGS) has provided a rapid and efficient platform for genome studies that has revolutionized the diagnostic, prognostic, and therapeutic realms of myeloid malignancies. Current NGS myeloid panels incorporate 20-50 genes and can identify mutations in the vast majority of patients. In MDS, mutations of *ASXL1*, *ETV6*, *EZH2*, *RUNX1* and *TP53* were found to be independently associated with decreased survival. Of these, recent investigations have suggested that the mutational status of *TP53* is the most important negative prognostic factor in MDS patients. *TP53* mutations are detected in up to 20% of MDS cases, are associated with higher risk MDS, complex cytogenetics and poor overall survival (OS) compared to wild-type *TP53* MDS.

*TP53* mutations are strongly associated with poor outcomes in azacitidine treated patients. In addition, Bejar and colleagues recently confirmed decreased OS in *TP53*-mutant MDS patients treated with HMA without effect on response rates. Lastly, mutations of *TP53* strongly predict for lack of benefit to allogeneic bone marrow transplantation, which represents the only curative option for patients with MDS. This study highlights the prognostic importance of *TP53* mutations as patients with complex karyotype without *TP53* mutation had similar survival to patients with normal karyotype.

Overall, *TP53*-mutant MDS and AML patients have a median OS ranging from 5-9 months with 8 months representing the best estimate when restricting to MDS and oligoblastic AML (20-30% blasts). Together, these data highlight the dismal outcomes of *TP53*-mutant MDS patients and the dire need for the development of novel therapeutic strategies, particularly in this patient population.

## 2.3 APR-548

[figure not shown]
[figure not shown]
[figure not shown]
[figure not shown]

113  
114  
115

A large black rectangular redaction box covers the majority of the page content, from approximately y=111 to y=250 and x=111 to x=886.

A thick black horizontal bar at the bottom of the page, likely a placeholder for a logo or footer content.

### 2.3.1 Pharmacology and Mode of Action

[figure not shown]
### 2.3.2 Pharmacokinetics

A series of horizontal black bars of varying lengths, likely a redacted document. The bars are arranged vertically, with some being full lines and others being shorter segments. The lengths of the bars decrease as they move down the page.

### 2.3.3 Safety Pharmacology and Toxicology

A series of horizontal black bars of varying lengths, likely representing redacted text or a visual effect.

## 2.4 Azacitidine

Azacitidine is a nucleoside metabolic inhibitor that was approved for the treatment of patients with MDS of all subtypes in 2004 by the US FDA and for higher-risk MDS, chronic myelomonocytic leukemia (CMML) and AML with 20% to 30% blasts and multi-lineage dysplasia by the European Medicines Agency in 2009.

Azacitidine is a pyrimidine nucleoside analogue of cytidine that exerts its antineoplastic activity by hypomethylation of the DNA, which has a cytotoxic effect on abnormal hematopoietic cells. At low doses, azacitidine is able to induce reactivation of cell cycle-regulating genes that were initially silenced due to hypermethylation, which may induce cell differentiation, reduce proliferation and/or increase apoptosis of the daughter cells.

In two early trials by Silverman et al. (CALGB 8421 and CALGB 8921), median duration of response (DOR) was 14.7 and 17.3 months for patients treated with i.v. versus subcutaneous (s.c.) azacitidine, respectively. In the randomized, multicenter, phase 3, CALGB 9221 trial, patients with MDS who received azacitidine 75 mg/m^2/day s.c. for 7 days every 28 days had a significantly higher overall response rate (ORR) than those receiving supportive care alone (60% versus 5%). Hematological response data from these three trials were retrospectively reanalyzed using International Working Group (IWG) 2000 criteria. Among 99 patients who received azacitidine and 41 patients who received supportive care (without subsequently crossing over to azacitidine), the ORR (CR plus partial remission [PR] plus hematological improvement [HI]) was 47% versus 17%, with CR rates of 10% versus 0%, PR rates of 1% versus 0% and HI rates of 36% versus 17%.

In the randomized, open-label, multicenter, phase 3 trial AZA-001, in adults with higher-risk (i.e., IPSS intermediate-2-risk or high-risk classification) MDS/AML, median OS was

significantly better with s.c. azacitidine 75 mg/m^2 per day for 7 days every 28 days than with conventional care (21.1 versus 11.5 months;  $p=0.0045$ ) and with azacitidine versus low-dose cytarabine (24.5 versus 15.3 months;  $p=0.0006$ ). The median time to AML transformation was significantly longer in patients receiving azacitidine than in those receiving conventional care (17.8 versus 11.5).

Azacitidine is rapidly absorbed after s.c. or i.v. administration with a  $V_d$  of  $76 \pm 26$  L and a  $T_{1/2}$  of  $41 \pm 8$  minutes.  $C_{max}$  is reached after about 30 minutes. Azacitidine and its metabolites are known to be substantially excreted by the kidney, and the risk of adverse reactions to this drug may be greater in patients with impaired renal function. Urinary excretion is the primary route of elimination; the cumulated urinary excretion is 85% of radioactive dose with less than 1% recovered in feces over 3 days.

Azacitidine undergoes spontaneous hydrolysis in aqueous solution and is deaminated by cytidine deaminases. Preliminary data indicate that drug-drug interaction with APR-548 as perpetrator are not likely, but the drug-drug interaction will be investigated as part of the current trial.

## 2.5 Rationale for the Starting Dose and Maximum Exposure of APR-548

A series of horizontal black bars of varying lengths. The longest bar is at the bottom and contains a series of smaller black rectangles of different widths, suggesting a grid or a series of data points.

•

## 2.6 Rationale for Combination of APR-548 with Azacitidine

[REDACTED]  
[REDACTED]  
[REDACTED].

## 2.7 Rationale for Dose of APR-548 in Combination with Azacitidine

[REDACTED]  
[REDACTED]  
[REDACTED]  
[REDACTED]  
[REDACTED]  
[REDACTED]  
[REDACTED].

## 2.8 Potential Risks and Benefits

[figure not shown]
### 2.8.1 Potential Risks

[REDACTED]  
[REDACTED]  
[REDACTED]  
[REDACTED]  
[REDACTED]  
[REDACTED].

[REDACTED]  
[REDACTED]  
[REDACTED].

[REDACTED]  
[REDACTED]  
[REDACTED]  
[REDACTED]  
[REDACTED]  
[REDACTED]  
[REDACTED].

[REDACTED]  
[REDACTED]  
[REDACTED]  
[REDACTED]  
[REDACTED]  
[REDACTED]  
[REDACTED].

[REDACTED]

[REDACTED]  
[REDACTED]  
[REDACTED]  
[REDACTED]  
[REDACTED]

[REDACTED]

[REDACTED]  
[REDACTED]  
[REDACTED]  
[REDACTED]  
[REDACTED]  
[REDACTED]

[REDACTED] ions [REDACTED] [REDACTED] [REDACTED] [REDACTED]

[REDACTED]

[REDACTED]

[REDACTED] could be considered to originate from the CNS should be treated as clinically indicated.

[REDACTED]

## 2.8.2 Potential Benefits

Patients with *TP53*-mutant MDS have a poor prognosis and unmet medical need. APR-548 has demonstrated *in vitro* synergy with azacitidine, a standard of care agent for *TP53*-mutant MDS. The purpose of this clinical trial is to define the safety and tolerability of APR-548 in combination with azacitidine in patients with *TP53*-mutant MDS and to determine preliminary efficacy. Given that *TP53*-mutant MDS patients have a limited life expectancy and lack of effective treatments, the benefit/risk assessment supports the use of APR-548 in this trial.

## 2.9 Characteristics of a Well-Conducted Trial

The following characteristics of an adequate and well-conducted trial will be implemented:

1. The investigators will be well qualified by scientific training and experience.
2. Detailed electronic eCRFs will be completed for every subject.
3. Requirements for institutional ethics review as set forth by the appropriate IRB/IEC, Title 21 CFR Part 56, the European Union Directive 2001/20/EC and its associated Detailed Guidances, European Union GCP Directive 2005/28/EC, the ICH Guideline for GCP, Sections 3 and 4, and the terms of the Declaration of Helsinki (2013), will be followed.
4. Requirements for informed consent in accordance with institutional guidelines, FDA requirements as specified in Title 21 CFR, Part 50, the European Union Directive 2001/20/EC and its associated Detailed Guidances, European Union GCP Directive 2005/28/EC, the ICH Guideline for GCP, Section 4.8, and the terms of the Declaration of Helsinki (2013), will be followed.
5. Safety data will be recorded and evaluated.
6. Routine monitoring visits will be conducted by the Sponsor's representative to ensure data accuracy.
7. Drug accountability will be strictly maintained.
8. This trial will be conducted according to GCP, the protocol and applicable regulatory requirements.

## 2.10 Subject Population

This study will enroll adult male and female subjects of age  $\geq 18$  years with documented diagnosis of *TP53*-mutant MDS, according to the World Health Organization (WHO) classification (<20% blasts). Subjects with relapsed/refractory *TP53*-mutant MDS will be allowed in the study.

## 3.0 TRIAL OBJECTIVES AND PURPOSE

### 3.1 Primary Objective

To investigate the PK, safety and tolerability of APR-548 as monotherapy and in combination with azacitidine and determine the recommended phase 2 dose (RP2D) of APR-548 in subjects with *TP53*-mutant MDS.

### 3.2 Secondary Objectives

1. To assess preliminary clinical activity of APR-548 administered in combination with azacitidine.
  - a. Rate of CR
  - b. Duration of CR (DOCR)
  - c. ORR
  - d. Duration of ORR
  - e. Rate of and time to development of AML transformation, as defined by WHO criteria
  - f. OS
  - g. Relapse-free survival (RFS)
  - h. Rate of transition to hematopoietic stem cell transplant (HSCT)
  - i. Rate of red blood cell (RBC) and/or platelet transfusion independence (TI) for 8 weeks
2. To characterize PK of APR-548 after single and multiple dosing when given orally (p.o.)
3. To evaluate the PK drug-drug interaction between APR-548 and azacitidine.

### Exploratory objectives:

1. To assess PD markers of APR-548 in blood and bone marrow samples.
2. To assess molecular markers of response to APR-548 in baseline and serial blood samples and bone marrow samples.

## 4.0 TRIAL DESIGN

### 4.1 Overview of Trial Design

This is an open-label FIH phase 1 clinical trial that will assess safety, PK, and clinical activity of p.o. administered APR-548 in combination with azacitidine for the treatment of *TP53*-mutant MDS.

Treatment will be administered on an outpatient basis but may be administered in the inpatient setting for subjects who are hospitalized and meet criteria for study treatment. No investigational or commercial agents or therapies other than those described below may be administered with the intent to treat the subject's disease under study.

The study is guided by a 3+3 dose escalation of APR-548 in the safety run-in monotherapy and the safety run-in combination therapy portions.

APR-548 will initially be given p.o. QD during Days 1 – 4 of a 28-day safety run-in period. The first 3 subjects enrolled on each dose level will be evaluated for a 28-day DLT safety follow-up period prior to enrolling additional subjects on that dose level or prior to dose escalation. If no DLT is observed, subjects will proceed to the safety run-in combination therapy portion with APR-548 in combination with azacitidine administered s.c. or i.v. at the standard dose of 75 mg/m^2 on Days 1-7 of the 28-day cycle. The first 3 subjects on each dose level of the combination with APR-548 and azacitidine will be evaluated for a 28-day DLT safety follow-up period prior to enrolling additional subjects on that dose level or prior to dose escalation with the combination treatment.

During the safety run-in of the monotherapy and during the safety run-in of the combination treatment, each subject within the dose level will be evaluated for safety and tolerability of APR-548. APR-548 dose escalation will be guided by an assessment of safety, PK and PD data, and may proceed until DLTs are observed or the pre-defined maximum exposure of APR-548 in plasma (average Cmax and AUC 8 µM and 16 µM·h, respectively) is reached, or the minimum biologically effective dose (mBED) is achieved (the dose at which no further incremental effect on markers of apoptosis and/or proliferation is observed, in the monotherapy safety run-in only). The DRT, consisting of the Medical Monitor, Site Principal Investigators, retina specialist and other clinical research personnel that the Sponsor deems appropriate, will review available PK, PD and safety data for each 3-6 subject cohort in both the safety run-in for the monotherapy and the combination portions, and increases in dose will be guided by the observed safety, PK and PD data, until the RP2D is determined. The RP2D of APR-548 will be defined as the lowest of:

1. mBED in the monotherapy safety run-in,
2. The dose that achieves the pre-defined level of maximum exposure in the monotherapy or combination therapy safety run-ins, or
3. The dose at which there are <2 DLTs in 3-6 subjects in a cohort, in the monotherapy

or combination therapy safety run-ins.

Up to 10 subjects may be enrolled at the RP2D per decision of the DRT to gain additional confidence in the RP2D.

Subjects in Cohort 1 will receive a starting dose of 50 mg/day (Dose level 1). If there is a DLT in  $\leq 1/3$  subjects in Cohort 1, Cohort 1 will be expanded to enroll 3 more subjects. If  $\geq 2$  subjects out of the total 3-6 subjects have a DLT, dose escalation will not occur. If  $\leq 1$  DLT occurs in the 6 subjects treated at that dose level, the subsequent subject group (Cohort 2) will be enrolled upon DRT review of data as described above, at the APR-548 dose of 150 mg/day (Dose level 2). If  $\geq 2$  of 6 subjects at a dose level have a DLT, or if the pre-defined maximum exposure of APR-548 in plasma is reached or the mBED is achieved (in monotherapy safety run-in only), then dose escalation ceases. This study will evaluate up to 6 dose levels. Any subsequent dose escalation will not exceed 100% and will follow the same principle as described above. The table below shows the planned dose levels based on the expected APR-548 human PK and under the assumption that the doses are well tolerated. Once the RP2D is established, if only 3 subjects were treated at the RP2D, an additional 3 subjects will be included in the cohort and if  $\leq 1$  DLT occurs in the 6 subjects treated at that dose level, the RP2D will be defined.

The [REDACTED]

[REDACTED]

[REDACTED]

[REDACTED]

The DRT will also review any other emergent toxicities that are not explicitly defined by the DLT criteria to determine if any warrant a DLT designation.

If the dose escalation of the 28-day safety run-in proceeds more rapidly than the combination portion such that the dose of APR-548 undergoing evaluation in the 28-day safety run-in exceeds that being assessed in the combination portion, the subject will receive the dose of APR-548 currently being assessed for safety in the combination portion. If a subject in the 28-day safety run-in period has a dose reduction of APR-548 due to AE, the subject will proceed with Cycle 1 of the combination portion with the reduced dose of APR-548 in combination with standard dose azacitidine.

Following discussions with the DRT, the schedule of APR-548 may be modified, including multiple daily and weekly doses, based on available PK, PD, and safety data.

Subjects in the 28-day safety run-in period and in Cycle 1 of the combination portion who miss  $\geq 25\%$  of APR-548 doses for a nonmedical reason (e.g., subject's preference) or noncompliance will be replaced.

Subjects in the combination portion may receive a higher dose of APR-548 than originally assigned after completion of at least two cycles of combination therapy at the assigned dose level if safety data for a higher dose level of APR-548 in combination with azacitidine have been reviewed by the DRT and concluded as safe.

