	
escalation in the next cohort. The mBED of APR-548 will be defined as the dose at which no further incremental effect on markers of apoptosis and/or proliferation is observed. Dose escalation of the monotherapy safety run-in may proceed until the earliest occurrence of 1) the mBED is reached, 2) ≥2 DLTs in 3-6 subjects in a cohort, or 3) average APR-548 exposure of exceeds 1/10 of the no-observed-adverse-effect level (NOAEL) or 1/5 the NOAEL for an individual subject (NOAEL relates to the dose level at which no AEs including eye toxicity were observed in the dog). For subjects that proceed from the monotherapy safety run-in to the combination safety run-in, if the dose escalation of the 28-day safety run-in proceeds more rapidly than the combination portion such that the dose of APR-548 undergoing evaluation in the 28-day safety run-in exceeds that being assessed in the combination portion, the subject will receive the dose of APR-548 currently being assessed for safety in the combination portion. If a subject in the 28-day safety monotherapy run-in period has a dose reduction of APR-548 due to an AE, the subject will proceed with the reduced dose of APR-548 in the combination safety run-in of APR-548 with standard dose azacitidine. Dose escalation of the combination safety-run in may proceed until the earliest occurrence of 1) ≥2 DLTs in 3-6 subjects in a combination cohort, or 2) average APR-548 exposure in a combination cohort exceeds 1/10 of the NOAEL or 1/5 the NOAEL for an individual subject. In addition, the dose of APR-548 in the combination portion will not exceed the mBED established in the monotherapy safety run-in.
 
  
 Cohort	Dose Levela	APR-548 (mg)b	Expected Human PK	Safety Factor to APR-548 exposure at NOAEL in Dogs	
 
 Cmax (μM)	AUC (h·μM)	Cmax (74.3 μM)	AUC (160 h·μM)	
   
 1	1 (Starting dose)	50 mg/day	1.2	2.7	62	59	
 
 2	2	150 mg/day	3.7	8	20.1	20	
 
 3	3	300 mg/day	7.4	16	10	10	
 
 4	4	450 mg/dayc	11.1	24	6.7	6.7	
 
 	Max dose	Average limit	8	16	9.2	10	
 
 	Max dose	Individual limit	15	32	5	5	
  
 
aAdditional cohorts may be added guided by the DRT, with maximum exposure not exceeding pre-specified threshold  bDose levels are preliminary. Exact dose levels will be determined on safety and exposure data  cExpected Human PK will be updated based on ongoing PK analysis and dose level of 450 mg/day will only be administered if expected human PK is below pre-specified thresholds after this update.
 
Subjects in the combination portion may receive a higher dose of APR-548 than originally assigned after completion of at least two cycles of combination therapy at the assigned dose level if safety data for a higher dose level of APR-548 in combination with azacitidine have been reviewed by the DRT and concluded as safe.
 
Subjects in the 28-day safety run-in periods (monotherapy or combination portions) who miss ≥25% of APR-548 doses for a nonmedical reason (e.g., subject's preference) or noncompliance will be replaced.
	Cohort	Dose Level a	APR-548 (mg) b	Expected Human PK		Safety Factor to APR-548 exposure at NOAEL in Dogs		C max (μM)	AUC (h·μM)	C max (74.3 μM)	AUC (160 h·μM)	1	1 (Starting dose)	50 mg/day	1.2	2.7	62	59	2	2	150 mg/day	3.7	8	20.1	20	3	3	300 mg/day	7.4	16	10	10	4	4	450 mg/day c	11.1	24	6.7	6.7		Max dose	Average limit	8	16	9.2	10		Max dose	Individual limit	15	32	5	5

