**Table 5. APR-548 dose management guidelines for nausea, vomiting, and/or diarrhea adverse events**

Worst toxicity grade	Dose modification guidelines for APR-548 *
Grade 1	
 
Maintain dose level of APR-548 and monitor subject; provide supportive care measures as clinically indicated.
 

Grade 2	
 
Interrupt APR-548 dosing and monitor subject; treat promptly.
 
Resume at current dose level if toxicity resolves to Grade <math>\leq</math> 1 or baseline, with or without use of supportive care measures, within 72 hours of onset.
 
If toxicity does not resolve to Grade <math>\leq</math> 1 within 72 hours despite maximal medical intervention(s), then reduce APR-548 by 1 dose level once the toxicity resolves to
 

		
Grade ≤1 or baseline.
 
 
• If unable to reduce APR-548 dose, discuss with study Medical Monitor before resuming or discontinuing treatment.
 
• For subsequent doses of APR-548, pre-medication with prophylactic supportive therapy should be given if clinically indicated.
 

Grade 3	1 st occurrence	
 
• Interrupt APR-548 dosing and monitor subject; treat promptly.
 
• Resume at current dose level if toxicity resolves to Grade ≤1 or baseline, with supportive care measures, within 72 hours of onset.
 
• If toxicity does not resolve to Grade ≤1 within 72 hours despite maximal medical intervention(s), then reduce APR-548 by 1 dose level once the toxicity resolves to Grade ≤1 or baseline.
 
• If unable to reduce APR-548 dose, discuss with study Medical Monitor before resuming or discontinuing treatment.
 
• For subsequent doses of APR-548, pre-medication with prophylactic supportive therapy should be given.
 

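### When monotherapy is two or more dose levels ahead, a subject dose-reduced for an adverse event has two different combination entry doses and no stated order of priority

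*Combined protocol and SAP*

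**What the plan says.** Section 4.1 and the synopsis (Treatment Plan) carry the same two rules, one straight after the other.

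- **Lag rule.** Trigger: the monotherapy dose under evaluation is higher than the combination dose under assessment. Then "the subject will receive the dose of APR-548 currently being assessed for safety in the combination portion".
- **Reduction rule.** Trigger: the subject's APR-548 dose was cut for an adverse event (AE) during monotherapy. In Section 4.1, "the subject will proceed with Cycle 1 of the combination portion with the reduced dose of APR-548 in combination with standard dose azacitidine"; in the synopsis, "the subject will proceed with the reduced dose of APR-548 in the combination safety run-in".

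Both are mandatory, and neither is made subject to the other. Other text that bears on the point:

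- The synopsis gives the combination its own stopping rules, among them "≥2 DLTs in 3-6 subjects in a combination cohort". It also caps the combination dose at the minimum biologically effective dose found in monotherapy.
- Section 4.1 allows for a level that was cleared on three subjects: "Once the RP2D is established, if only 3 subjects were treated at the RP2D, an additional 3 subjects will be included in the cohort".
- Section 4.1 lets a subject move up after at least two combination cycles, "if safety data for a higher dose level of APR-548 in combination with azacitidine have been reviewed by the DRT and concluded as safe".
- The Section 5.2 tables reduce APR-548 one level at a time. In Table 5, if a Grade 2 or first Grade 3 gastrointestinal event has not settled within 72 hours, "then reduce APR-548 by 1 dose level once the toxicity resolves to" Grade 1 or less, or baseline.
- Footnote c of the synopsis dose table makes the fourth level conditional: "dose level of 450 mg/day will only be administered if expected human PK is below pre-specified thresholds after this update".

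**The concern.** One subject can meet both triggers at once, and the text then gives two doses. The subject concerned has already had a dose-reducing AE on APR-548 alone, in a first-in-human trial, and is about to add azacitidine. A site that lets the later and more specific sentence govern would choose the reduction rule, which is the higher dose whenever the two differ.

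The sentence has practical force because APR-548 is given only on Days 1-4. Under Table 5, an event that starts on Day 2 reaches the end of its 72-hour wait on Day 5, after the last monotherapy dose. A reduction of that kind is therefore usually first given in combination Cycle 1, and this sentence fixes it.

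**Working it through.** The plan states no figure to reproduce. The check applies both rules to every pairing on the planned ladder.

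**Inputs.** Dose levels are 50, 150, 300 and 450 mg/day (synopsis dose table). A reduction is one level (Section 5.2 tables). Write m for the monotherapy level and c for the combination level under assessment.

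**Formulas.** The lag rule gives level c, and applies only if m > c. The reduction rule gives level m − 1. They agree when m − c = 1 and differ when m − c ≥ 2. At m = c the lag rule is not triggered, so only the reduction rule speaks.

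| Monotherapy / combination (mg) | Gap in levels | Lag rule (mg) | Reduction rule (mg) | Ratio |
|---|---|---|---|---|
| 150 / 50 | 1 | 50 | 50 | 1 |
| 300 / 150 | 1 | 150 | 150 | 1 |
| 450 / 300 | 1 | 300 | 300 | 1 |
| 300 / 50 | 2 | 50 | 150 | 3 |
| 450 / 150 | 2 | 150 | 300 | 2 |
| 450 / 50 | 3 | 50 | 300 | 6 |

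In every row where they differ, the reduction rule is above the level being assessed with azacitidine.

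**Exposure at 300/50.** From the synopsis dose table, expected Cmax is 3.7 against 1.2 µM (ratio 3.7/1.2 = 3.1) and expected AUC is 8 against 2.7 h·µM (8/2.7 = 3.0). For the 450 mg rows the tabled AUC of 16 at 300 mg should not be used. If 450 mg is open at all, its updated average AUC is below 16, so under dose proportionality 300 mg is below 16 × 300/450 = 10.7 h·µM.

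**Can a two-level gap occur?** No visible text limits how far monotherapy may lead. Two routes exist.

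1. *The combination steps back.* Take 28-day blocks with no delay, and let monotherapy 50 and 150 mg and combination 50 mg each clear on three subjects. Monotherapy 300 mg then runs days 56-84. Combination 50 mg runs days 28-56 and combination 150 mg days 56-84. If combination 150 mg closes on day 84 with two or more dose-limiting toxicities (DLTs), three more subjects are due at combination 50 mg, just as the monotherapy 300 mg subjects arrive. A subject reduced from 300 mg gets 50 mg by the lag rule and 150 mg, the level just closed, by the reduction rule.
2. *The combination expands at both 50 and 150 mg while monotherapy reaches 450 mg.* This is the 450/150 row. It is narrower, because it needs two expansions and a 450 mg level. That level's currently expected AUC of 24 h·µM exceeds the average limit of 16, so it opens only if updated pharmacokinetics come in lower.

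**Does other visible text rank the rules?** The cap at the minimum biologically effective dose limits the dose but does not rank them. The DRT condition governs a rise after at least two combination cycles, not the entry dose. The 3+3 rules govern when a cohort may escalate. None of these decides the entry dose of a dose-reduced subject.

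**The case against.** The strongest reply is that the surrounding design already excludes the higher dose. The combination is its own 3+3, with a 28-day observation of the first three subjects at each level, and escalation stops at two or more DLTs. Starting a subject above the level under assessment would run against that. A reduction rule is also naturally read as a further cut, not as leave to exceed the lag-rule dose. This shows the likely intent and makes an error less probable, but the intent has to be inferred.

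Second, an AE-driven dose reduction is itself a DLT unless clearly and solely due to the disease (Section 5.1.3), and Section 4.1 sends subjects on to the combination when no DLT is seen. That might seem to empty the affected group. It does not, because the reduction rule expressly sends such subjects in, and a bar would leave that rule almost without use. The group is nonetheless small.

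Third, route 1 depends on one of two readings of cohort size. The expansion wording in Section 4.1 and the synopsis, and the sample size of six per cohort, can be read as requiring six subjects before escalation; other wording allows three. If combination 50 mg already holds six, no level need be open, and the lag rule supplies no dose. The conflict as described then does not arise, but the entry dose still needs stating. Route 1 also assumes no delay for DRT review, and both cohorts would be due for review at the same time.

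Fourth, 150 mg is not extreme: its expected AUC of 8 h·µM is half the average limit and 20-fold below the dog no-effect exposure. That limits the harm in the 300/50 case.

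Fifth, a block of Section 4.1 and all of Section 2.7 are redacted, and Figure 1 is not shown. The readable synopsis repeats both rules without a tie-break, but the finding can cover only the visible text.

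**Conclusion.** The point holds as a minor drafting ambiguity with a safety aspect. At a lead of two or more levels the two rules give different doses, and the reduction rule gives the higher one: 3 times at 300/50, 2 times at 450/150 and 6 times at 450/50. This rests on a one-level reduction from the monotherapy dose under evaluation. The 300/50 case alone establishes it.

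A reader might infer more than the documents support:

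- *That the synopsis and Section 4.1 contradict each other.* They match; the same conflict sits inside each.
- *That the protocol intends treatment at a closed or unassessed combination dose.* The cohort rules and the DRT condition point to the lower dose. The fault is that the operative sentence does not say so.
- *That the conflict is likely.* It needs a two-level gap and a dose-reduced subject arriving during it, and the documents give no rate for this. The chance that a combination cohort closes, under some assumed DLT risk, would not measure it. DRT or Medical Monitor review would probably catch the higher dose.
- *That the recommended phase 2 dose is affected.* Nothing here shows that.

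**What to change.** In both Section 4.1 and the synopsis (Treatment Plan), replace the end of the dose-reduction sentence with: *the subject will proceed at the lower of the reduced dose and the APR-548 dose currently being assessed in the combination portion or, if no combination level is open, the highest combination dose the DRT has concluded is safe.*

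The second limb covers a combination portion that has stopped with no cohort enrolling. Nothing changes at a one-level lead, where the rules already agree. The existing stop at two or more DLTs in three to six subjects stays as written.

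The cost is one sentence in two places, with no added subjects or visits.
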